“Any local reaction” is “yes” for Days 1-10 after vaccination if at least 1 local reaction is present on at least 1 day, is “no” if the subject reports “no” or missing for every local reaction on each of Days 1-10 after vaccination, and is “missing” if every local reaction on every day is missing.

Duration of local reaction is calculated as the date of the last reported reaction minus the date of the first reported reaction, plus 1. If the local reaction has not resolved by the last date in the e-diary, then the resolution date recorded in the case report form (CRF) will serve as the date of the last reported reaction. If the resolution date is missing from the CRF, then duration will be set to missing. Duration will be missing for subjects without the indicated local reaction. Duration will not be calculated for “any local reaction.”

The onset day for a local reaction is the first day of the reaction, even if the reaction later becomes more severe. The onset day for “any local reaction” will be the first day of any local reaction, regardless of severity. Onset day will be missing for subjects without the indicated local reaction.

Local reactions recorded on or after the day of surgery will be excluded from all analyses.

Numeric scores for the systemic events are the same as for local reactions: none = 0, mild = 1, moderate = 2, and severe = 3. The systemic event grading scale is presented in Table 3.

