**Table 4. Temperature Categories**

Categories
38.0-38.4°C (100.4-101.1°F)
38.5-38.9°C (101.2-102.0°F)
39.0-40.0°C (102.1-104.0°F)
>40.0°C (>104.0°F)

“Any fever” is defined as  $\geq 38.0^{\circ}\text{C}$ .

Antipyretics or pain medication used to treat symptoms will also be collected in the e-diary. Response values will be “yes” and “no.”

The derivations for the systemic event endpoints are the same as for local reactions. “Any systemic event” will include fever  $\geq 38.0^{\circ}\text{C}$ , but exclude the use of antipyretic or pain medication.

The systemic event endpoints are:

1. Maximum grade during Days 1-10 after vaccination, for each systemic event.
2. Mild, moderate, or severe response during Days 1-10 after vaccination, for each systemic event.

3. Maximum grade during Days 1-10 after vaccination, for “any systemic event.”
4. Proportion of subjects with a moderate or severe systemic event on each day.
5. Duration in days, but not for “any systemic event.”
6. Onset of the indicated systemic event in days.
7. Onset of “any systemic event” in days.

The endpoints for fever are:

1. Maximum fever category during Days 1-10 after vaccination.
2. Proportion of subjects with any fever category on each day.
3. Duration in days, but only for  $\geq 38.0^{\circ}\text{C}$ .
4. Onset in days, but only for  $\geq 38.0^{\circ}\text{C}$ .

Duration and onset will not be calculated for antipyretic or pain medication.

A baseline assessment of fatigue, headache, muscle pain, and joint pain over the previous month will be collected before vaccination. Grading will be none = 0, mild = 1, moderate = 2, and severe = 3. Only 1 baseline assessment per indicated systemic event will be obtained.

Systemic events recorded on or after the day of surgery will be excluded from all analyses.

Statistical methodology for local reactions and systemic events is described in [Section 8.1.2.3](#).

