Missing values will not be imputed for any immunogenicity, safety, demographic, or colonization variables. However, immunogenicity values less than LLOQ will be set as  $0.5 \times \text{LLOQ}$  for the analysis.

Subjects who are vaccinated but do not undergo the index surgery will not have a Day 1 visit. Their last day in the study will be labeled Day -1.

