### **8.1.2.3. Methodology for Local Reactions and Systemic Events After Vaccination**

Binary endpoints (eg, any redness on Days 1-10 after vaccination) will be summarized with proportions by vaccine group. Two-sided 95% CIs will be compiled for all proportions. Vaccine groups will be compared using method of Miettinen and Nurminen.

The number and proportion of subjects with indicated local reaction or systemic event on each day will be compiled by vaccine group, but vaccine groups will not be statistically compared.

Vaccine groups will be compared in duration and onset using the Mann-Whitney test, 2-sided.

Vaccine groups will be compared in baseline assessments of fatigue, headache, muscle pain, and joint pain using the Fisher exact test, 2-sided.

NNH will be calculated for both any local reaction and any systemic event. A 95% CI will be obtained for each NNH by obtaining a 2-sided 95% CI on the difference in proportions using the method of Chan and Zhang, then reciprocating the upper and lower limits. The difference in proportions is defined as SA4Ag minus placebo.

1. If the difference in proportions and both confidence limits are less than zero, then the results will be presented as number needed to benefit (NNB) = xx.x (xx.x, xx.x), with the negative signs omitted.
2. If the difference in proportions and both confidence limits are greater than zero, then the results will be presented as NNH = xx.x (xx.x, xx.x).

3. If the CI brackets zero, then the results will be presented as NNB (if negative) or NNH (if positive) = xx.x (NNH = xx.x, NNH = xx.x), with any negative signs omitted.

Baseline assessments will be summarized by proportion of any response (ie, mild, moderate, or severe) and by proportion that are moderate or severe. Vaccine groups will be compared using the Fisher exact test, 2-sided.

Statistical analyses for local reactions and systemic events are summarized in [Section 8.2.2.3](#).

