**8.2.2.3. Local Reactions and Systemic Events**

A listing will be created for local reactions and systemic events (including fever) still present on the last day that the subject’s e-diary was completed. This will not include subjects with both redness and swelling <5 caliper units on the last day. The number of days since vaccination will be computed as the stop date minus the date of vaccination, plus 1. If the event is still ongoing, then the stop date will be set to missing, as will the number of elapsed days. The listing will include site, subject, injection site (for local reactions only), vaccine group, name of local reaction or systemic event, vaccination date, stop date, ongoing (yes/no), and number of elapsed days. The listing will be sorted by vaccine group, site, subject, and name of local reaction or systemic event. The listing will include the date when the reaction resolves, or ends as “ongoing.”

Subjects reporting any severe local reaction and any severe systemic event on the same day will be identified. Their 10-day local reactions and systemic events will be listed, as well as resolution of events persisting beyond 10 days.

The proportions of subjects completing the e-diary each day will be compiled, as well as the categories “Days 1-4,” “Days 1-7,” and “All days (Days 1-10).” Subjects who fail to complete the e-diary only because of early surgery, ie, surgery on the 10th day after vaccination or earlier, will still be considered to have completed the e-diary as of the day before surgery.

For example, a subject who completes the e-diary on every day up to the 8th day, and then has surgery on the 9th day, will be considered to have completed “All days (Days 1-10).”

The proportions of subjects with at least 1 e-diary entry on or after the day of surgery will be compiled by vaccine group. Entries in e-diaries on or after the day of surgery will be excluded from analysis. These proportions will quantify what proportion of subjects may have additional local or systemic entries that were not included in the analysis.

Per protocol Section 4.1, the e-diary need not be completed on the day of surgery. The proportions of subjects with surgery on Days 1, 2, 3, etc, will be compiled to explain incomplete e-diaries.

All analyses will be performed in the safety population. No subgroup analyses are proposed.

Analyses for local reactions and systemic events are summarized in Table 20.

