**Table 20. Summary of Analyses for Local Reactions and Systemic Events**

Endpoint	Population	Statistical Method	Model/ Covariates/ Strata	Missing Data	Interpretation/ Comments
Proportions of maximum mild, moderate, severe, and any reaction over Days 1-10 after vaccination (redness, swelling, pain, plus any local reaction)	Safety	Fisher exact	Vaccine group	See Section 6.2.3	Assess reactogenicity
Proportions of subjects with the indicated reaction (redness, swelling, pain, plus any local reaction) on each day	Safety	Descriptive only	Vaccine group	N/A	No statistical test
Proportions of subjects with moderate or severe indicated reaction (redness, swelling, pain, plus any local reaction) on each day	Safety	Descriptive only	Vaccine group	N/A	No statistical test
Duration of local reaction in days, but only for pain, swelling, and redness	Safety	Mann-Whitney	Vaccine group	N/A	Assess reactogenicity
Onset day of local reaction for pain, swelling, redness, and any local reaction	Safety	Mann-Whitney	Vaccine group	N/A	Assess reactogenicity
Baseline assessment of fatigue, headache, muscle pain, and joint pain over the previous month	Safety	Fisher exact	Vaccine group	N/A	Assess reactogenicity

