**Table 20. Summary of Analyses for Local Reactions and Systemic Events**

Endpoint	Population	Statistical Method	Model/ Covariates/ Strata	Missing Data	Interpretation/ Comments
Proportion of maximum mild, moderate, severe, and any systemic event over Days 1-10 after vaccination (fever, vomiting, diarrhea, fatigue, headache, muscle pain, joint pain, plus any systemic event); also antipyretic/pain medication use	Safety	Fisher exact	Vaccine group	See Section 6.2.3	Assess reactogenicity
Proportions of subjects with the indicated systemic event each day, plus any systemic event	Safety	Descriptive only	Vaccine group	N/A	No statistical test
Proportions of subjects with moderate or severe indicated systemic event on each day	Safety	Descriptive only	Vaccine group	N/A	No statistical test
Duration of systemic event/fever, but not for any systemic event	Safety	Mann-Whitney	Vaccine group	N/A	Assess reactogenicity
Onset of systemic event/any systemic event/fever	Safety	Mann-Whitney	Vaccine group	N/A	Assess reactogenicity
Subjects reporting any severe local reaction and any severe systemic event on the same day	Safety	N/A	Vaccine group	N/A	Listing of Days 1-10, including day of interest
Listing of unresolved reactions still present on the last e-diary day	Safety	N/A	Vaccine group	N/A	
Completing the e-diary each day	Safety	N/A	Vaccine group	N/A	
Completing the e-diary on Days 1-10	Safety	N/A	Vaccine group	N/A	Categories for days completed are 100%, 75%-<100%, 50%-74%, 25%-49%, and <25%
One or more e-diary entries on or after the day of surgery	Safety	N/A	Vaccine group	N/A	
Proportion of subjects with surgery on Days 1, 2, 3, etc, after vaccination	Safety	N/A	Vaccine group	N/A	Days with zero proportions may be omitted; eg, there is no expectation of subjects' receiving surgery on the day

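### Reactions and systemic events unresolved at the end of the e-diary with no CRF stop date get a missing duration, so right-censored events leave the arm comparison of duration

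*SAP*

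**What the plan says.** SAP 6.2.3 defines the duration of a local reaction as the last reported date minus the first, plus 1. For a reaction that outlasts the diary it reads "If the local reaction has not resolved by the last date in the e-diary, then the resolution date recorded in the case report form" as the end date. It then adds: "If the resolution date is missing from the CRF, then duration will be set to missing". Subjects who never had the reaction also carry a missing duration, so the same code covers both situations. For systemic events the section says "The derivations for the systemic event endpoints are the same as for local reactions".

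The comparison is in SAP 8.1.2.3: "Vaccine groups will be compared in duration and onset using the Mann-Whitney test, 2-sided". Table 20 repeats it in two rows, "Duration of local reaction in days, but only for pain, swelling, and redness" and "Duration of systemic event/fever, but not for any systemic event". Both use the safety population and the Mann-Whitney test, and both mark missing data as not applicable. SAP section 7 rules out a repair by imputation: "Missing values will not be imputed for any immunogenicity, safety, demographic, or colonization variables". No censored-data or sensitivity analysis of duration is planned.

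Protocol 7.2.1.1 asks the site to obtain stop dates for symptoms ongoing on the last completed diary day and to enter them in the CRF. Protocol 6.3.1.1 repeats the request at the pre-surgery diary review. Under protocol 7.2.1.5 a fever is measured daily until it resolves.

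**The concern.** An event present on the last diary date with no later stop date is partly observed: it is known to have lasted at least from its onset to that date. Only the upper end is unknown, which is right-censoring. The SAP treats it as if nothing were known and leaves it out. Whether an event is left out depends on whether resolution was seen, and that is the outcome being measured, so the exclusion is informative.

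Two things are at stake. Reported durations are too short in both arms. And if one arm has more events that persist beyond the diary, part of that difference is removed before the test is run.

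**Working it through.** The plan gives no sample size, expected duration, power or expected missing share for this comparison, so there is no figure to reproduce. The check has two parts.

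**1. Trace of the rule.** Event unresolved at the last diary date → CRF date used if present, otherwise duration missing (SAP 6.2.3, local and systemic) → no imputation (SAP 7) → Mann-Whitney on the non-missing durations (SAP 8.1.2.3, Table 20). Nothing in this chain uses the known minimum duration.

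**2. Illustration of size.** All inputs below are assumptions except the 10-day diary:
- 300 subjects with the event per arm, onset on diary days 1 to 3.
- Short events geometric with mean 2.5 days; long events last more than 10 days, with mean 20.
- Long-event share 15% (SA4Ag) and 5% (placebo).
- A fraction q of events unresolved at Day 10 has no CRF stop date, with the same q in both arms.
- Two-sided Mann-Whitney at 0.05 (the SAP states no level for this test), 2000 replicates.

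True means: 0.85 × 2.5 + 0.15 × 20 = 5.125 days for SA4Ag, and 0.95 × 2.5 + 0.05 × 20 = 3.375 days for placebo. The simulation returns 5.13 and 3.38.

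| q | Dropped, SA4Ag / placebo | Mean of durations analysed, SA4Ag / placebo | Rejection, SAP rule | Rejection, undated events kept and ranked longest |
|---|---|---|---|---|
| 0 | 0 / 0 | 5.13 / 3.38 | 59% | 59% |
| 10% | 1.6% / 0.6% | 4.90 / 3.28 | 53% | 60% |
| 25% | 4.0% / 1.5% | 4.54 / 3.14 | 39% | 58% |
| 50% | 8.0% / 3.0% | 3.88 / 2.90 | 25% | 59% |
| 100% | 16% / 6% | 2.40 / 2.41 | 5% | 57% |

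The simulation error of a rejection rate near 59% is about √(0.59 × 0.41 / 2000) = 1.1 points, so the last column is flat within error.

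The mean difference analysed shrinks from 5.13 − 3.38 = 1.75 days at q = 0 to 4.54 − 3.14 = 1.40 at q = 25% and 3.88 − 2.90 = 0.98 at q = 50%. With long-event shares of 20% and 10%, the SAP rule gives 59%, 53%, 42%, 23% and 4% over the same values of q, against 58–59% when the events are kept.

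With equal arms (5% and 5%), rejection under the SAP rule stays at 4.7–6.1%, so type I error is not visibly disturbed. Mean duration is still understated in both arms: 3.4 days falls to 2.9 at q = 50% and 2.4 at q = 100%.

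Ranking undated events as longest stands in for keeping them in the comparison. The gain from a log-rank test itself was not simulated.

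**The case against.** The strongest reply is that the rule should seldom apply. The protocol asks twice for stop dates and follows fever to resolution, and protocol 1.2.5 reports that reactions in earlier studies of healthy adults resolved within a few days. With 10% of stop dates missing, the illustrated loss is only about 6 points. The endpoint is also minor: protocol 2.2.1 lists numbers and proportions as primary safety endpoints, and duration has no hypothesis or power target. All of this stands and sets the priority. It does not make the rule sound, since the loss that remains is still tied to non-resolution.

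Some stronger readings are tempting, but the documents do not support them:
- **That the longest events as such drop out.** A long event with a CRF date stays in at full length. A dropped event need not be long either: the last diary entry can fall before Day 10, and an event that began that day has a known minimum of one day.
- **That a difference in persistence vanishes from the report.** SAP 8.1.2.3 and Table 20 tabulate daily proportions by arm, and SAP 8.2.2.3 lists events still present on the last diary day with vaccine group and ongoing status.
- **That this listing repeats the error.** It does say "If the event is still ongoing, then the stop date will be set to missing, as will the number of elapsed days", but its elapsed days run from vaccination. They are a listing item, not the duration variable.
- **That the loss is total.** Suppose 25% of all SA4Ag events and 15% of placebo events are undated and the rest are equally distributed. Ranking the undated events longest gives P(SA4Ag longer) = 0.25 × 0.85 + 0.5 × 0.75 × 0.85 + 0.5 × 0.25 × 0.15 = 0.55, with about 56% power at 300 per arm, against 0.50 under the SAP. But the 0.50 follows by construction, because the whole difference was placed in the dropped events, and nothing in the documents supports those shares.
- **That unresolved pain or fatigue at Day 10 is common in these patients.** This is plausible, since protocol 7.2.1.4 grades such symptoms at baseline, but it is not quantified, and pre-existing symptoms are expected in both randomised arms.

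**Conclusion.** The point holds within limits. Setting duration to missing for unresolved, undated events discards a known lower bound and makes exclusion depend on the outcome. It biases duration downward in both arms and pulls an arm difference in persistence toward zero. Incidence, maximum severity, onset and daily proportions are not affected.

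The size cannot be fixed from the documents. Under the assumptions above, rejection falls from 59% to 53%, 39% and 25% when 10%, 25% and 50% of stop dates are missing. With good stop-date collection the effect is small; it becomes material only if collection is poor. Minor priority.

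**What to change.** In SAP 6.2.3, 8.1.2.3 and Table 20, treat an event with no resolution date as right-censored at the last date it was reported present. Compare arms with Kaplan-Meier estimates and a log-rank or Gehan-Wilcoxon test, and report the number censored by arm for each reaction and event. SAP 6.2.3 should also state how a CRF stop date on or after the day of surgery is used, because events recorded from that day on are excluded from all analyses.

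Do not place these events at their known minimum in an ordinary Mann-Whitney test. That treats a lower bound as an exact duration, can rank a late-onset ongoing event among the short ones, and stays biased downward.

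The cost is SAP wording and modest programming, with no new data. Two limits remain. A median may not be estimable if many events are censored. And the method assumes that undated events resolve like dated ones still ongoing at the same time, so the counts by arm are needed to judge the result.

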**Table 3. Systemic Event Grading Scale**

	GRADE 1 Mild	GRADE 2 Moderate	GRADE 3a Severe	GRADE 4b
Fatigue (Tiredness)	Does not interfere with activity	Some interference with activity	Prevents daily routine activity	Emergency room visit or hospitalization
Headache	Does not interfere with activity	Some interference with activity	Prevents daily routine activity	Emergency room visit or hospitalization
Vomiting	1 to 2 times in	>2 times in 24 hours	Requires intravenous	Emergency room visit

**Table 3. Systemic Event Grading Scale**

	GRADE 1 Mild	GRADE 2 Moderate	GRADE 3a Severe	GRADE 4b
	24 hours		hydration	or hospitalization
Diarrhea	2 to 3 loose stools in 24 hours	4 to 5 loose stools in 24 hours	6 or more loose stools in 24 hours	Emergency room visit or hospitalization
Muscle pain	Does not interfere with activity	Some interference with activity	Prevents daily routine activity	Emergency room visit or hospitalization
Joint pain	Does not interfere with activity	Some interference with activity	Prevents daily routine activity	Emergency room visit or hospitalization

- a. Subjects experiencing severe systemic events will telephone the study site. In the event that the subject does not call, the investigator will call the subject.
- b. Grade 4 assessment should be made by the investigator and recorded as an AE on the case report form.

Grade 4 assessments will not be recorded in the e-diary, but will be recorded as AEs on the CRF. Only an investigator is able to classify a subject’s systemic event as Grade 4, after physical examination of the subject or telephone contact with the subject. Any such systemic events will be recorded as AE on the CRF. In addition to their inclusion in the general AE analysis, these events will be listed and discussed separately as reactogenicity events.

Four categories are defined for analysis of body temperature (see Table 4).

**Table 4. Temperature Categories**

Categories
38.0-38.4°C (100.4-101.1°F)
38.5-38.9°C (101.2-102.0°F)
39.0-40.0°C (102.1-104.0°F)
>40.0°C (>104.0°F)

“Any fever” is defined as  $\geq 38.0^{\circ}\text{C}$ .

Antipyretics or pain medication used to treat symptoms will also be collected in the e-diary. Response values will be “yes” and “no.”

The derivations for the systemic event endpoints are the same as for local reactions. “Any systemic event” will include fever  $\geq 38.0^{\circ}\text{C}$ , but exclude the use of antipyretic or pain medication.

The systemic event endpoints are:

1. Maximum grade during Days 1-10 after vaccination, for each systemic event.
2. Mild, moderate, or severe response during Days 1-10 after vaccination, for each systemic event.

3. Maximum grade during Days 1-10 after vaccination, for “any systemic event.”
4. Proportion of subjects with a moderate or severe systemic event on each day.
5. Duration in days, but not for “any systemic event.”
6. Onset of the indicated systemic event in days.
7. Onset of “any systemic event” in days.

The endpoints for fever are:

1. Maximum fever category during Days 1-10 after vaccination.
2. Proportion of subjects with any fever category on each day.
3. Duration in days, but only for  $\geq 38.0^{\circ}\text{C}$ .
4. Onset in days, but only for  $\geq 38.0^{\circ}\text{C}$ .

Duration and onset will not be calculated for antipyretic or pain medication.

A baseline assessment of fatigue, headache, muscle pain, and joint pain over the previous month will be collected before vaccination. Grading will be none = 0, mild = 1, moderate = 2, and severe = 3. Only 1 baseline assessment per indicated systemic event will be obtained.

Systemic events recorded on or after the day of surgery will be excluded from all analyses.

Statistical methodology for local reactions and systemic events is described in [Section 8.1.2.3](#).

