7.2.1.4. Systemic Events

Prior to vaccination, subjects will consider whether they generally experience fatigue, headache, muscle pain, or joint pain. If so, the symptoms will be graded as mild, moderate, or severe and recorded in the e-diary as baseline symptoms. The Systemic Event Grading Scale in Table 10 will be used.

Starting on the day of vaccination, and for 10 consecutive days, postvaccination systemic events will be assessed by the subject each day, and if present, they will be graded as mild, moderate, or severe and recorded in the e-diary, using the grading scale in Table 10.

A subject with a severe/Grade 3 systemic event will be instructed to contact the investigator who will assess the reaction. In the event that the subject does not call, the investigator will call the subject.

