**Table 2. Local Reaction Grading Scale**

	GRADE 1 Mild	GRADE 2 Moderate	GRADE 3a Severe	GRADE 4b
Redness	5 to 10 caliper units (or measuring device units) 2.5 to 5.0 cm	11 to 20 caliper units (or measuring device units) 5.5 to 10.0 cm	≥21 caliper units (or measuring device units) ≥10.5 cm	Necrosis or exfoliative dermatitis b
Swelling	5 to 10 caliper units (or measuring device units) 2.5 to 5.0 cm	11 to 20 caliper units (or measuring device units) 5.5 to 10.0 cm	≥21 caliper units (or measuring device units) ≥10.5 cm	Necrosis b
Pain at injection site	Does not interfere with activity	Interferes with activity	Prevents daily activity	Emergency room visit or hospitalization

a. Subjects experiencing local reactions ≥21 caliper units (≥10.5 cm) will telephone the study site. In the event that the subject does not call, the investigator will call the subject.

b. Grade 4 assessment should be made by the investigator and recorded as an AE on the case report form.

Note: If the size of the redness and/or swelling falls between 2 caliper units, the higher caliper unit number will be recorded in the electronic diary (e-diary).

Numeric scores for the local reactions will be: none = 0, mild = 1, moderate = 2, and severe = 3.

Grade 4 will not be collected in the e-diary. Only an investigator is able to classify a subject’s local reaction as Grade 4, after physical examination of the subject or telephone contact with the subject. Any such local reactions will be recorded as AE on the CRF. In addition to their inclusion in the general AE analysis, these events will be listed and discussed separately as reactogenicity events.

The derived local reaction variables are:

1. Maximum grade during Days 1-10 after vaccination, for each local reaction.

2. Mild, moderate, or severe response during Days 1-10 after vaccination, for each local reaction.
3. Duration in days, but not for “any local reaction.”
4. Onset of the indicated local reaction in days.
5. Onset of “any local reaction” in days.

The mild, moderate, or severe response during Days 1-10 after vaccination is “yes” if present on at least 1 day.

A given local reaction is “yes” for Days 1-10 after vaccination if present on at least 1 day, is “no” if the subject reports any combination of “no” and “missing” on each of Days 1-10 after vaccination, and is “missing” if every day is missing.

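### The pre-vaccination grade for fatigue, headache, muscle pain and joint pain is collected but not used in the systemic-event analysis; stratifying by it would cost nothing and make the results sharper and easier to read

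*SAP*

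**What the plan says.** **Baseline.** Protocol Section 7.2.1.4 asks subjects before vaccination whether fatigue, headache, muscle pain or joint pain is usual for them, and adds: "If so, the symptoms will be graded as mild, moderate, or severe and recorded in the e-diary as baseline symptoms". The scale is the one used for the daily diary (Protocol Table 10). SAP Section 6.2.3 repeats this: "A baseline assessment of fatigue, headache, muscle pain, and joint pain over the previous month will be collected before vaccination", scored 0 to 3, with one assessment per symptom.

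**After vaccination.** The same protocol section says that "postvaccination systemic events will be assessed by the subject each day, and if present, they will be graded as mild, moderate, or severe". Neither document requires the symptom to be new or worse. The first endpoint in the SAP 6.2.3 list is "Maximum grade during Days 1-10 after vaccination, for each systemic event". On derivation the SAP says: "The derivations for the systemic event endpoints are the same as for local reactions". A local reaction counts as a yes "for Days 1-10 after vaccination if present on at least 1 day". Onset is the first day reported, and duration runs from first to last report.

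**Use of the baseline grade.** SAP Section 8.1.2.3 plans a summary by arm (any grade; moderate or severe) and a balance test: "Vaccine groups will be compared in baseline assessments of fatigue, headache, muscle pain, and joint pain using the Fisher exact test, 2-sided". Table 20 lists this as its own row. The outcome row, "Proportion of maximum mild, moderate, severe, and any systemic event over Days 1-10 after vaccination", has vaccine group as its only model term. The NNH is computed on any systemic event. SAP Section 8.2.2.3 proposes no subgroup analyses for these data.

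**The concern.** The counting rule is borrowed from injection-site reactions, which have no pre-vaccination state. It fits less well for four symptoms that do have one, recorded on the same scale. A subject with stable moderate joint pain who reports it on one diary day is counted as having moderate joint pain after vaccination, whatever the product did. Such subjects are foreseeable here: Protocol Section 3.2.2.1 permits indications such as facet joint arthritis, disc disease and spinal stenosis.

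Systemic events within 10 days are a primary safety endpoint (Protocol Section 2.2.1). Three things are at stake:

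- whether the absolute rates can be read as reactogenicity;
- whether onset and duration, which go into Mann-Whitney tests, describe a response to vaccination or the first diary report of an old complaint;
- whether precision already paid for in data collection is left unused.

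A between-arm test at baseline addresses none of these, because it makes no link between a subject's own baseline and later grades.

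**Working it through.** The documents state no baseline prevalence, expected reactogenicity rate or power for systemic events, so there is no plan figure to reproduce. What follows is illustration. Only the 1:1 allocation and the planned total of about 6000 (about 3000 per arm, Protocol Section 3.1) come from the documents.

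**1. What the planned risk difference estimates.** Assume a share *b* symptomatic at baseline. Of these, 90% report the symptom after vaccination in either arm. Among symptom-free subjects, 15% report it on placebo and 25% on SA4Ag. With *b* = 0.5:

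- SA4Ag: 0.5×0.90 + 0.5×0.25 = 57.5%
- Placebo: 0.5×0.90 + 0.5×0.15 = 52.5%
- Risk difference: 5.0 points, which is the average of 0 points (symptomatic) and 10 points (symptom-free): 0.5×0 + 0.5×0.10
- Share of placebo events in baseline-symptomatic subjects: 0.45/0.525 = 86%

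The 5 points are correct for this mixed population. The tables as planned cannot show the two components.

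**2. Precision.** Multiply each variance by *n* per arm.

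- Unstratified: the sum over arms of P(1−P)
- Stratified: *b*×2×0.9×0.1 + (1−*b*)×(0.15×0.85 + 0.25×0.75) = 0.18*b* + 0.315(1−*b*)

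| *b* | Unstratified | Stratified | Ratio |
|---|---|---|---|
| 0.3 | 0.4814 | 0.2745 | 0.57 |
| 0.5 | 0.4938 | 0.2475 | 0.50 |
| 0.7 | 0.4274 | 0.2205 | 0.52 |

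At *b* = 0.5 and 3000 per arm the standard error is √(0.4938/3000) = 0.0128 unstratified and √(0.2475/3000) = 0.0091 stratified. The ratio does not depend on *n*.

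The saving equals *b*(1−*b*) times the sum over arms of the squared gap between symptomatic and symptom-free subjects. At *b* = 0.5 this is 0.25×(0.75² + 0.65²) = 0.246, matching 0.4938 − 0.2475. If baseline grade did not predict later reports, the gap and the saving would both be zero.

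**3. A second model.** Let background symptoms occur with probability *b* and vaccine-caused symptoms with independent probability *r*. Placebo is then *b*, SA4Ag is 1−(1−*b*)(1−*r*), and the risk difference is *r*(1−*b*). With *r* = 0.10:

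| *b* | Risk difference | NNH |
|---|---|---|
| 0.10 | 0.090 | 11.1 |
| 0.40 | 0.060 | 16.7 |
| 0.60 | 0.040 | 25.0 |

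Among subjects without the background symptom the difference is 0.10 and the NNH 10.0.

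**4. How much is background?** In this model the background share of SA4Ag-arm events is *b*/[*b* + *r*(1−*b*)]. It runs from 15% (*b* = 5%, *r* = 30%: 0.05/0.335) to 99% (*b* = 80%, *r* = 5%: 0.80/0.81). The documents do not say where in that range this trial lies.

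**5. The composite.** If the four symptoms were independent, at least one would be present from background alone in 1−(1−*b*)⁴ of subjects: 34% at *b* = 10% each, 59% at 20%, 87% at 40%. This is how any systemic event, and its NNH, inherit the issue.

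**The case against.** The strongest reply is that nothing planned is wrong. The safety objective is to describe (Protocol Section 2.2). Protocol Section 9.5 asks for maximum severity over 10 days with descriptive statistics, and the SAP delivers that. Allocation is 1:1 against placebo, so background symptoms fall on both arms. There is no hypothesis, power target or decision rule for reactogenicity. In step 1 the raw difference is still clear: 0.05/0.0128 gives z of about 3.9, or about 2.8 with an assumed 1500 per arm. That matters because SAP Section 8.1.3.5 records that enrollment stopped after the interim analysis. The baseline table gives group-level context, and SAP Section 8.2 allows further exploratory analyses. All of this stands. It limits the point to interpretation and precision.

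Two stronger readings are tempting, and the documents support neither.

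- **That the endpoint mostly measures chronic symptoms.** This needs a baseline prevalence and a vaccine-attributable rate. Neither is given, and step 4 shows how wide the answer is. Fever, vomiting and diarrhea have no baseline assessment at all.
- **That a true ratio of 0.25/0.15 = 1.67 is reported as 57.5/52.5 = 1.10.** No ratio is planned for systemic events, the two figures describe different populations, and both rest on assumed inputs.

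A count of grades above baseline also has real weaknesses. It compares one previous-month grade with a maximum over 10 days, so ordinary fluctuation can look like worsening. A subject graded severe at baseline cannot exceed that grade, because Grade 4 is not recorded in the e-diary. Finally, the e-diary wording and study reference manual are not available, so an instruction there to report only new or worse symptoms cannot be excluded.

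**Conclusion.** The point holds as a missed, cost-free improvement to a primary safety analysis. It is not an error that biases the arm comparison. The recorded baseline grade plays no part in any post-vaccination systemic-event derivation, comparison or NNH. Absolute rates, onset and duration for four symptoms therefore include pre-existing complaints, and the risk difference mixes two kinds of subject and is less precise than it need be.

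The documents do not allow the size to be fixed. The variance ratio of 0.50–0.57 assumes 30–70% symptomatic at baseline, 90% recurrence in both arms, and 15% against 25% among symptom-free subjects. The 90% figure builds in no vaccine effect among symptomatic subjects. The gain shrinks to nothing as baseline grade becomes less predictive. The efficacy design is untouched.

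**What to change.** In SAP Section 8.1.2.3 and Table 20, for fatigue, headache, muscle pain and joint pain:

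1. Stratify the Miettinen-Nurminen risk difference by baseline grade (none, mild, moderate, severe), with a stated rule for collapsing sparse strata. Table 20 still names the Fisher exact test for these rows while Section 8.1.2.3 names Miettinen-Nurminen; settle this in the same edit.
2. Show the post-vaccination proportions by baseline grade and arm.
3. Keep the raw summary as the protocol endpoint, with the raw count of any systemic event and its NNH. Add a footnote that the raw rates, onset and duration include symptoms present before vaccination.
4. Optionally add a supplementary row for maximum grade above baseline grade. Label it with its limits: a single previous-month grade against a 10-day maximum, and no possible increase for subjects severe at baseline. It should not replace the raw composite or its NNH.

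The cost is a few lines of SAP text and one table. The baseline grades are already in the e-diary, so no new data are needed. If arm-level safety data have already been seen, label the additions as made after that point.
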